## Eligibility for the prevalence survey (outcome evaluation)

[figure not shown]
- 1. Aged 15 years or older on the date of enumeration for the prevalence survey
- 2. Capable of giving informed consent.

# 8) Study Procedures

#### **Preparation**

The screening team (four fieldworkers) will conduct a series of meetings with local health and government officials to brief them on the procedures and to generate political and community support. The residents of the Ap will be informed about the survey by announcements broadcast over loudspeakers and banners deployed throughout the subcommune. Finally, we will hold a public meeting to explain the study and to answer any questions from members of the local community.

#### **Enumeration**

#### **Testing phase**

#### Initial Household visit

Screening for latent tuberculosis infection and for TB will be undertaken by a pair of study team members in participants' households.

[figure not shown]
Participants aged 5 years or older at the date of enumeration (or their parents or guardians) will be asked to provide written informed consent for testing (see "PCF1 – Test") (see page 33 for details of consent procedure).

The following procedures will be performed for all individuals who have provided consent to participate in screening:

- 1. Take a digital photograph of the face of the participant (for the purpose of subsequent re-identification). This will be stored in a secure online database.
- 2. Participants will be asked if they have any current symptoms of TB (cough, sputum or haemoptysis, swelling in neck or weight loss) (see "Symptom screening questionnaire").
- 3. A tuberculin skin test (TST) will be placed using the standard Mantoux technique.

# Household visit 48-96 hours after TST injection

Field workers will return to the household 48-96 hours after placement of the TST to read the size of the induration. The induration will be digitally photographed and measured (perpendicular to the long axis of the forearm) using the 'ballpoint technique. pen' Callipers will be used to measure the size of the reaction. Reactions > 10mm (or > 0mm for participants known to be HIV +ve) will be classified as

positive. ("Tuberculin test forms - placement and reading").

Screened participants who have a positive TST or who report symptoms of TB will be asked to:

- 1. Provide a single, spontaneously expectorated sputum specimen, if possible. The study team member will explain how to expectorate sputum using a pictorial guide. All sputum specimens will be transferred in a foam-insulated cool box to our laboratory in Ca Mau City (see "Sputum Xpert form"). At the laboratory, specimens will be tested using Xpert MTB/RIF Ultra, or equivalent test, within 48 hours of collection. If the initial Xpert test is reported as "invalid", the test will be repeated.
- 2. Provide information on concomitant medications taken in the past seven days or planned to take in the next seven days, and on presence of known liver disease or HIV infection, drug allergy and consumption of alcohol will be acquired using a questionnaire (see "Pre-treatment Assessment Form fieldworker"). The fieldworker will consult with the study medical officer if the participant reports he / she is taking any medication. The participants will not be required to cease any of their current medications to participate in this study.
- 3. In addition, women aged 15-45 years will be asked if they are pregnant or are attempting to fall pregnant or are breastfeeding (see "Pregnancy and lactation screening form").

Patients who report that they are HIV +ve and have TST reaction > 0mm will be referred to the HIV program for further management.

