## Assessment for LTBI treatment phase

#### Evaluation at central location

Participants who have a positive TST or who report symptoms of TB will be asked to have:

 A chest Xray in a mobile x-ray van located at central location, in or near their village. Images will be exported to our online data repository. Images will either be read by an onsite radiologist or initially assessed using a validated artificial intelligence program for detection of TB. In the latter case, those images flagged as abnormal will be re-read by an onsite radiologist (see "Chest radiograph report form"). Chest xrays will be classified by each reader as: "consistent with TB", "abnormality, other than TB" and "normal or no significant abnormality". Women who state they are pregnant or attempting to fall pregnant will be excluded from chest radiography.

2. Baseline measurement of body weight, blood pressure and blood tests for liver function tests (LFT), full blood count (FBC). The physical examination findings will be recorded on the "Body weight, Blood Pressure forms".

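### The skin-test cut-off depends on known HIV status, but the only HIV question described is put to people who already have a positive test or TB symptoms

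*Protocol*

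**What the plan says.** The steps appear in this order in section 8 of the protocol.

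- **Initial Household visit.** The list is introduced by "The following procedures will be performed for all individuals who have provided consent to participate in screening". It has three items: a facial photograph, a symptom question ("Participants will be asked if they have any current symptoms of TB (cough, sputum or haemoptysis, swelling in neck or weight loss") and placement of the TST. HIV status is not among them.
- **Household visit 48-96 hours after TST injection, classification.** "Reactions > 10mm (or > 0mm for participants known to be HIV +ve) will be classified as" positive. The person reading the test therefore needs HIV status to apply the rule.
- **Same visit, next steps.** A numbered list opens with "Screened participants who have a positive TST or who report symptoms of TB will be asked to". Item 1 is a sputum specimen for Xpert testing. Item 2 is the Pre-treatment Assessment Form, through which "presence of known liver disease or HIV infection, drug allergy and consumption of alcohol will be acquired using a questionnaire".
- **Same visit, closing sentence.** "Patients who report that they are HIV +ve and have TST reaction > 0mm will be referred to the HIV program for further management".
- **Evaluation at central location.** The chest radiograph uses the same entry condition: "Participants who have a positive TST or who report symptoms of TB will be asked to have".

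**The concern.** The HIV answer is an input to the TST classification, yet the described procedure collects it after the classification, and only from people who have passed it or who have symptoms. The lower cut-off changes the TST result only for known HIV-positive people with small reactions. Within that group, those without symptoms are never asked.

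At stake are a work-up for active TB and a referral that the protocol intends for these people. Uniformity is also affected: whether the lower cut-off is used would depend on who discloses unprompted and on which fieldworker thinks to ask.

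**Working it through.** No power or sample-size figure is involved. The check traces each type of known HIV-positive, TST-read participant through the written steps.

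| Reaction | TB symptoms | Asked about HIV? | Outcome as written |
|---|---|---|---|
| Above the general cut-off | Either | Yes, through the positive TST | Sputum, radiograph and HIV referral follow |
| Above 0 mm, not above the general cut-off | Yes | Yes, through the symptom route | Sputum, radiograph and HIV referral follow |
| Above 0 mm, not above the general cut-off | No | No | Classified negative; no sputum, radiograph or referral, unless status is volunteered or captured elsewhere |

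Other places where HIV status might become known earlier:

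- The eligibility criteria for the testing phase (section 7) cover age, consent and current TB treatment. HIV is not mentioned.
- The Check criteria (section 8) do not ask it, and they apply only after a person has been found eligible for LTBI treatment.
- The household census for the prevalence survey, said to follow the enumeration described earlier, collects name, year of birth or age, sex and phone number.

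None of these supplies HIV status before the test is read.

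**Scale.** The only HIV figure in the protocol is in *Study setting and population*: 19 co-infections in 2017, when 1,045 pulmonary TB cases were reported. 19 / 1,045 = 1.82%, which reproduces the stated 1.8%. This is HIV among reported TB cases, so it does not give HIV prevalence among residents.

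For orientation only, take the 74,800 eligible adults per group from *Sample size and study power* as a stand-in for those screened (the intervention also covers ages 5 to 14). Two inputs are assumptions that the documents do not give: 0.1% to 0.5% of adults know they are HIV-positive, and 5% to 20% of those fall in the third row.

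- Low end: 74,800 × 0.001 = 75 people; 74,800 × 0.001 × 0.05 = 3.7.
- High end: 74,800 × 0.005 = 374 people; 74,800 × 0.005 × 0.20 = 74.8.

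That is roughly 4 to 75 people, at most 75 / 74,800 = 0.1% of adults in the intervention arm.

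**The case against.** The strongest reply is that the forms are not shown. The classification sentence points to placement and reading forms for the skin test, and a form that implements an HIV-dependent threshold is a natural place for an HIV field. A Manual of Procedures is also cited, and the text under the Enumeration heading is absent from the copy reviewed. It therefore cannot be stated as fact that the fieldworker has no HIV information. This stands, and it limits confidence. It does not remove the point, because the protocol assigns the HIV question by name to a different form given to a restricted group. If an earlier form does ask, the text still needs a line saying so.

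A second reply is that the referral sentence ("Patients who report that they are HIV +ve and have TST reaction > 0mm will be referred to the HIV program for further management") stands outside the numbered list and could apply to anyone whose test is read. That reading is possible. The sentence still depends on the participant reporting their status, and no described step elicits that report from asymptomatic people with small reactions. Nor does it provide the sputum test or radiograph.

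A third reply is that known status means status already on record. The protocol describes no record linkage, and its own referral sentence relies on self-report.

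The reply that few people are affected is accepted.

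**Conclusion.** The ordering defect is in the text. As written, the lower cut-off cannot operate for asymptomatic people with small reactions unless they volunteer their status or a form not shown records it. The consequence is a missed active-TB work-up and a missed HIV program referral for a group that is probably small. The documents cannot size it, and the effect on the primary endpoint is slight. It is worth correcting for participant safety and for consistent application of the protocol's own rule.

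A reader might infer more than this, and the documents do not support it:

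- *That HIV is asked only after a positive test.* Symptomatic people are asked whatever their reaction size.
- *That nearly everyone the rule is meant to catch is missed.* The symptom route and voluntary disclosure both capture some, and nothing in the documents gives the split.
- *That 1.8% measures the affected group.* It describes reported TB cases.
- *That trial LTBI treatment is lost.* This cannot be settled, because the protocol contradicts itself. The section 7 criteria for the treatment phase admit known HIV-positive people with any reaction above 0 mm, whereas *TB preventive treatment in those with LTBI but without active TB* (section 8) requires that the person is not known to be HIV-positive.

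**What to change.** Move the existing known-HIV question from the Pre-treatment Assessment Form to the initial household visit, or put it to every screened participant at the reading visit before the TST is classified. Ask it in private, with an option to decline, and record the answer where the stated threshold is applied. If a form already does this, say so in the protocol and name the form.

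The cost is one question moved between forms and a sensitive item put to more people in their homes, hence the privacy and opt-out provisions. Thresholds, later management and sample size stay as they are.

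Separately, reconcile the section 7 and section 8 statements on whether known HIV-positive people are eligible for LTBI treatment in the trial. Which statement should stand is a clinical decision for the sponsor.

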### **Eligibility criteria for treatment of LTBI phase**

- 1. Meet eligibility criteria for testing and consented to screening; AND
- 2. Tuberculin skin test (TST) reaction size  $\geq$  10mm (or > 0mm if known to be HIV +ve) AND
- 3. Either no abnormality consistent with TB on chest radiograph OR abnormal radiograph but two sputum specimens are culture negative for *M. tuberculosis*
- 4. Not pregnant or planning to be pregnant in next 6 months
- 5. No important potential drug interactions with the intervention regimen, defined by attending medical officer in accordance with a schedule.
- 6. No known allergy or hypersensitivity to the active substance or any of the ingredients of the study drugs
- 7. Has not completed a course of treatment for TB within the preceding two years.
- 8. Serum transaminases (AST and ALT) are both < 3 x upper limit of normal
- 9. No severe or life-threatening illness that is considered by the attending medical officer to make treatment for LTBI inappropriate.

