# *Further assessment of pregnant women, those attempting to fall pregnant and those who are breastfeeding*

Women who say they are pregnant or who say they are attempting to fall pregnant will not be referred for chest radiograph or for consideration for treatment of LTBI. However, if they meet the symptom or TST criteria for screening for active TB, they will be asked to provide a single sputum specimen for Xpert testing, as described above.

Women who are breastfeeding, but who are not currently pregnant or trying to become pregnant, will be referred for chest radiograph and counselled about their risk of TB. However, they will not be considered for treatment of LTBI.

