#### Medical Review

The study doctor will conduct a medical review prior to commencing TB preventive treatment (see "Medical assessment – baseline") for eligible participants who meet one or more criteria, defined as above

The objectives of the medical review are as follows.

- 1. To resolve any medical issues that require resolution as a result of the checks (symptom screen and blood tests) performed at baseline. If this cannot be done based on the information available at the time of the initial assessment, it is expected that the trial doctor will refer the patient to an appropriate clinic or other medical facility. If the participant has an acute illness (unrelated to TB) at the time of medical review, LTBI treatment may be delayed for up to 8 weeks from that date. If the patient's symptoms persist after 8 weeks, the participant will not be eligible for treatment of LTBI in the current phase.
- 2. Decide, in consultation with the participant, whether the participant should receive treatment for LTBI. Among the relevant considerations are the following:
  - a. Participants who have significant liver function abnormalities defined as an AST or ALT level greater than or equal to three times higher than the

Upper Limit of Normal (ULN) will not be offered treatment. They will be offered referral to a liver clinic.

- b. Participants who are regularly taking medications that interact with rifamycins, where the interactions cannot easily be managed, will not be offered treatment (see Appendix to Manual of Procedures).
- c. If, as a result of this assessment, it is apparent that the participant has another severe or life-threatening illness, he or she will not be offered treatment for LTBI. This will be at the discretion of the trial medical officer.
- 3. If it is decided that the participant should receive treatment for LTBI, define whether he or she is in the low- or high-risk monitoring for adverse events below).

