### **Indications for cessation of TB preventive treatment**

If a participant experiences one or more of the conditions/situations listed below, the Investigator will permanently discontinue study drugs

- 1) Participants deprived of freedom by an administrative or court order
- 2) SAE-related to the study drug.
- 3) Diagnosed with (and treated for) active TB
- 4) Pregnancy reported by the participant

TEST AND TREAT TO END TB Protocol, V2.0 14th September 2021 5) Onset of a condition that would have made the participant ineligible for commencing TB preventive treatment.

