#### Follow-up the post-treatment period

The end of treatment date will be either

- The date on which the 12th dose of treatment is taken or
- 16 weeks after treatment initiation

whichever comes first.

The final visit should be scheduled two weeks after the "end of treatment" date.

At this visit

• Interview the participant using the "Symptom Screening prior to Administering Medications" questionnaire. If the participant responds positively to any of the

TEST AND TREAT TO END TB Protocol, V2.0 14th September 2021 symptoms on the checklist, follow instructions in **Adverse event management** and submit the **eCRF "Adverse events**" form within 24 hours (even if unsure about whether it is an adverse event). If the Treatment Officer is unsure about whether a participant has had an Adverse Event, or whether Active TB should be investigated, discuss with the Medical Advisor by telephone.

• Complete the "Close-out" form, recording the total medication the participant had during the treatment, any adverse event occurred and the outcomes of adverse event.

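### LTBI treatment excludes women planning pregnancy within 6 months, but the screening question as described covers only current pregnancy, a current attempt or breastfeeding, and no described visit step prompts the matching stopping rules

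*Protocol*

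**What the plan says.** Protocol Section 7, *Eligibility criteria for treatment of LTBI phase*, item 4, requires that a participant be "Not pregnant or planning to be pregnant in next 6 months". It sets no age range and does not mention breastfeeding.

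Section 8, *Household visit 48-96 hours after TST injection*, describes the question used in the field: "women aged 15-45 years will be asked if they are pregnant or are attempting to fall pregnant or are breastfeeding". The section *Further assessment of pregnant women, those attempting to fall pregnant and those who are breastfeeding* then acts on the answer: "Women who say they are pregnant or who say they are attempting to fall pregnant will not be referred for chest radiograph", nor considered for LTBI treatment. Breastfeeding women may have the radiograph but are also kept out of LTBI treatment. *Evaluation at central location* uses the same two categories, pregnant or attempting, to withhold radiography.

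The operational list in *TB preventive treatment in those with LTBI but without active TB* settles pregnancy and lactation by reference to the screening questionnaire and does not restate the 6-month criterion. *Check criteria*, which decides who sees a doctor before the first dose, has no pregnancy item. Anyone who meets none of its criteria starts treatment without that review.

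During treatment, *Indications for cessation of TB preventive treatment* requires permanent discontinuation for a pregnancy the participant reports (item 4) and for "Onset of a condition that would have made the participant ineligible for commencing TB preventive treatment" (item 5).

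**The concern.** An eligibility criterion protects participants only if the field procedure collects what is needed to apply it. Here the criterion looks 6 months ahead, while the question as described asks only about the present. The two differ for an identifiable group: women who intend a pregnancy within 6 months but have not begun trying. The criterion removes them and the operational steps do not.

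The stopping rules have a related gap. They depend on learning that a participant has become pregnant or otherwise ineligible, but the described visit steps contain no item that asks.

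What is at stake is participant safety and consistent application of the protocol. A treated woman in this group would be a protocol deviation under Section 7 and correctly handled under Section 8, so teams and auditors reading different sections would classify her differently.

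**Working it through.** The protocol gives no figure to reproduce for this point. The check sets the sections side by side and follows one participant through them.

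**1. The criterion against the operational text**

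| Place in the protocol | Women covered | Pregnancy intention covered | Breastfeeding |
|---|---|---|---|
| Section 7, treatment criterion 4 | any age | pregnant now, or planned within 6 months | not listed |
| Section 8, household visit after TST | aged 15-45 | pregnant now, or trying now | asked |
| Section 8, evaluation at central location | no age stated | pregnant now, or trying now (radiograph only) | not mentioned |
| Section 8, further assessment | no age stated | pregnant now, or trying now | no LTBI treatment |
| Section 8, operational eligibility list | as in the questionnaire | as in the questionnaire | as in the questionnaire |
| Section 8, check criteria | no item | no item | no item |

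Only Section 7 contains the 6-month period.

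**2. One participant followed through**

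Take a woman aged 15-45 with a TST reaction of at least 10 mm, a normal radiograph, normal blood tests, no regular medicines and no symptoms. She plans a pregnancy in three months and is not yet trying.

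- Section 7, criterion 4: ineligible, since three months lies within 6 months.
- Household visit question: she truthfully answers no to all three parts.
- Further assessment: no exclusion applies.
- Operational list: the questionnaire, as described, does not exclude her, and she meets the other conditions.
- Check criteria: none is met, so no doctor reviews her before treatment.
- Result: she may be offered 3HP and, if she consents, receive it.

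**3. Age**

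LTBI treatment is open from age 5 and criterion 4 has no age limit. The question is put only to women aged 15-45. Participants outside that range fall under the criterion but are not asked.

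**4. Breastfeeding**

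The Section 8 text excludes breastfeeding women from LTBI treatment. Nothing in the Section 7 list does. Here the operational text is the stricter of the two.

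**5. Stopping rules against visit steps**

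- First treatment visit (*Follow-up during the TB preventive treatment period*): identity, screening results, consent.
- Later visits (same section and *Symptom screening*): adverse events, assessed with a symptom checklist.
- *Dispense medication*: the dose is given if identity is confirmed and the symptom screen is negative or the Medical Advisor authorises it.

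No step asks about pregnancy or a new medicine. Cessation item 4 therefore relies on the participant volunteering the information, and no described step would bring a new interacting medicine to notice under item 5.

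**The case against.** **The forms are not shown.** The pregnancy and lactation screening form, the pre-treatment assessment form and the pre-dose symptom questionnaire may ask more than the protocol reports. This stands as a limit on the finding. It does not remove the contradiction: wherever Section 8 describes the question or its consequences, it uses the narrower wording. If the form already asks about 6 months, correcting the text is trivial.

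**Section 7 must be followed too.** That is true, so it would go too far to say that correct conduct of the trial necessarily treats excluded women. But the operational list states that those meeting all its conditions are eligible, and none of the described steps collects what criterion 4 needs.

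**Other safeguards exist.** Treatment has its own consent with written and oral explanation, adverse events are evaluated at visits, and pregnancies must be reported within 24 hours of staff learning of them. These reduce the risk. None asks about a planned pregnancy, and the reporting rule begins only once staff know.

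**Not repeating the questions is a design choice.** This is fair, and the point here is limited to stopping rules and visit steps that do not connect.

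**A stronger reading about medicines is not supported.** A reader might infer that the medicines question, covering "concomitant medications taken in the past seven days or planned to take in the next seven days", is likewise shorter than its criterion. That criterion, "No important potential drug interactions with the intervention regimen", has no time window for the question to fall short of. Nor is the question the only screen: the fieldworker consults the study medical officer about any reported medication, regular medicines trigger a doctor's review, and that review excludes interactions that cannot easily be managed. Seven days back plus seven forward is 14 days, so it is also wrong to say that anything taken less often than weekly is missed.

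**Nor is a percentage of treatment time left uncovered.** A reader might compare the 7-day look-ahead with the longest path to the end of treatment. The rule that "LTBI treatment may be delayed for up to 8 weeks from that date" applies only to acute illness found at medical review, and "16 weeks after treatment initiation" is a cap on a 12-dose course, so adding them describes an exception. A medicine once noted can be judged for the whole course, so such a ratio does not measure what was missed.

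**Conclusion.** The pregnancy criterion and its screening question contradict each other as written. Section 7 excludes a planned pregnancy within 6 months at any age, whereas Section 8 asks about and acts on pregnancy or a current attempt, with the question put at ages 15-45. Breastfeeding is handled differently in the two sections. Separately, the described visit and dispensing steps contain nothing that would prompt cessation items 4 and 5 for a pregnancy or a new medicine.

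The number affected cannot be calculated, because the protocol gives neither the number of treated women of childbearing age nor the share planning but not yet attempting pregnancy. For scale only: assume that the adult population treated matches the 74,800 per group in the sample-size section and that the 38% adult LTBI prevalence in the background applies. Then 0.38 × 74,800 = 28,424 adults of both sexes might have LTBI, before consent and exclusions. The affected group is an unknown, smaller part of that.

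The finding rests on the protocol's description of forms that are not shown. It concerns safety and consistency of conduct, with no bearing on the primary endpoint, sample size or analysis. It is worth correcting because the correction is cheap.

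**What to change.** Reconcile Section 7 criterion 4 with the household visit question, the radiography exclusion, the further-assessment text, the operational eligibility list and the pregnancy and lactation screening form. Criterion and question should cover the same women and the same period, and breastfeeding should be treated the same way throughout. Also reconcile cessation items 4 and 5 with the first-visit, symptom-screening and dispensing steps, so that the protocol shows how these rules come into play. This review does not say which window, age range or clinical rule is right; that is for the investigators and their clinical advisers.

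The cost is protocol and form wording. The small downside is that, depending on how the sections are reconciled, a few more participants may be excluded or referred for review.
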